5.2 Identifying comorbidities of interest

The nine T2-type comorbidities of interest (atopic dermatitis; allergic rhinitis; chronic rhinosinusitis; nasal polyps; urticaria; allergic conjunctivitis; food allergy; eosinophilic oesophagitis; and anaphylaxis) will be identified by the presence of a Read code for the condition in the patient record. Anaphylaxis will also be identified by the prescription of adrenaline. Appendix 3 lists conditions where there are existing Read code definitions and those which will be developed during the study.

5.3 Categorising comorbidity activity and severity

Many of the comorbidities can be further characterised as inactive or active, and mild or moderate/severe at the index date using prescribing and primary and secondary consultation data. A comorbidity will be defined as inactive in the year prior to the index date if it was not classified as active. Similarly, a comorbidity will be defined as mild in the year prior to the index date if it was not classified as moderate/severe.

Following a rapid review of the definitions applied by studies using routine patient data and prescribing guidelines, the following definitions were adopted.

Note on medications with more than one indication

The indication for a prescription may not be recorded as the time it is issued and some medications can be indicated for more than one of the comorbidities of interest. Following a review of the approaches used in other published studies, the diagnosis recorded closest in time to the initiation of the medication will be taken as the indication. Similarly, the reason for outpatient consultations is not routinely coded in HES data and individual hospital specialties may treat more than one of the comorbidities of interest (e.g. ENT treating both allergic rhinitis and chronic rhinosinusitis). Where this occurs we will attribute the outpatient consultation to the diagnosis recorded closest in time to the secondary care consultation.

Atopic dermatitis

Active: A primary or secondary care consultation in the previous year. Prescription of a topical corticosteroid in the previous year.

Moderate/severe: A primary or secondary care consultation in the previous year. Prescription of a medium- to high-potency topical corticosteroid in the previous year (see Appendix 6 for categorisation of topical corticosteroid preparations).

Allergic Rhinitis

Active: A primary or secondary care consultation in the previous year. Prescription of a nasal corticosteroid in the previous year.

Moderate/severe: A primary or secondary care consultation in the previous year. Three or more nasal corticosteroid in the previous year.

Chronic Rhinosinutis

Active: Always active as this is a chronic condition.

Moderate/severe: A primary or secondary care consultation in the previous year. Three or more nasal corticosteroid prescriptions in the previous year.

Nasal polyps

Active: Always active.

Moderate/severe: A primary or secondary care consultation in the previous year. Three or more nasal corticosteroid in the previous year. Polypectomy at any time.

Urticaria

Active: A primary or secondary care consultation in the previous two years. Prescription of an oral antihistamine in the previous year.

Moderate/severe: A primary or secondary care consultation in the previous year. A double or greater dose of an oral antihistamine at any time prior to the index date.

Allergic Conjunctivitis

Active: A primary or secondary care consultation in the previous year. Prescription of any topical eye drop in the previous year.

Moderate/severe: A primary or secondary care consultation in the previous year. Two or more prescriptions of any topical eye drop in the previous year.

Food Allergy

Active: Always active.

Moderate/severe: A primary care consultation in the previous year. A secondary care consultation in the past two years. A prescription for adrenaline in the past 30 months (adrenaline has an 18-month shelf life). Anaphylaxis at any time.

Eosinophilic oesophagitis

Active: Always active (as long-term treatment required).

Moderate/severe: Always categorised as moderate/severe (differentiation not appropriate).

Anaphylaxis

Active: Always active (there is always a risk of a subsequent episode).

Moderate/severe: A secondary care consultation, ER attendance or hospital admission in the past year. A prescription for adrenaline in the past 30 months (adrenaline has an 18-month shelf life).

Sources

[1] How much of a topical agent should be prescribed for children of different sizes? Andrew A. Nelson, Alicia D. Miller, Alan B. Fleischer, Rajesh Balkrishnan, Steven R. FeldmaJ Dermatolog Treat. 2006; 17(4): 224–228.

[2] UpToDate (<https://www.uptodate.com/home>).

[3] Rapid reviews to identify comorbidity definitions used in other studies using routine patient data (see Appendices 13 and 14).

[5] Lucendo AJ, Arias Á, Molina-Infante J, Arias-González L. The role of endoscopy in eosinophilic esophagitis: from diagnosis to therapy. Expert Review of Gastroenterology & Hepatology. 2017; 11(12): 1135-1149.

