4.0 Study population

4.1 Data sources

Phase 1: The Optimum Patient Care Research Database (OPCRD)

- Contains anonymous, longitudinal medical records for 5.3 million patients from about 700 primary care practices across the UK.
- Includes patient-level diagnostic, clinical and prescribing information.

Phase 2: The OPCRD and the Clinical Practice Research Datalink (CPRD).

- The CPRD includes linked primary and secondary care (HES) data for approximately 300 UK primary care practices.
- The HES records from the CPRD are required to identify secondary care service use and costs, and for some measures of disease severity.

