6.0 Statistical analysis

6.1 Sample size

Phase 1: Approximately 220000 OPCRDR patients with active asthma will be available for inclusion in this phase. Of these, approximately 85000 have moderate to severe asthma (GINA steps 4 & 5).

Phase 2: Approximately 220000 OPCRDR patients and 440000 CPRDR patients with active asthma will be available for inclusion in this phase (85000 moderate to severe from OPCRDR and 170000 moderate to severe from CPRDR). Approximately 260000 of the CPRDR patients will have linked secondary care data (HES): the HES records are required to identify secondary care service use and costs, and for some measures of disease severity.

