6.3 CONSORT chart

A CONSORT-type chart, describing the number and proportion of patients retained and excluded at each step of the inclusion/exclusion criteria will be generated for each study phase.

6.4 Demographic and clinical characteristics of patients at index date (phase 1 and 2)

Phase 1: The demographic and clinical characteristics at index date of patients included in the analysis will be tabulated: this will include the number and proportion of patients with each of the comorbidities of interest. For completeness, the number of patients with no comorbidities will also be reported. As it will not be possible to distinguish between inactive and active comorbidity and mild to moderate/severe comorbidity for all comorbidities of interest without linked HES data, this will be reported as the number of patients with active/inactive comorbidity.

Phase 2: A similar set of outputs will be produced for the second phase. In addition, the number and proportion of patients whose comorbidity is inactive, active, mild and

moderate/severe will be tabulated for each comorbidity using the primary care and linked HES data.

Patient characteristics at index date will be reported for the study population using the following conventions:

- Continuous variables will be summarised using descriptive statistics: n (non-missing sample size), percentage of non-missing, mean, standard deviation, median, inter-quartile range (25th and 75th percentile), maximum and minimum.
- For categorical measures, the frequency and percentages (based on the non-missing sample size) of observed levels will be reported.

Comorbidity prevalence will be estimated for each comorbidity cluster by dividing the number of patients in the cluster by the total number of patients eligible for inclusion in the study.

The ratio of observed to expected cases for each comorbidity cluster will be estimated by dividing the observed prevalence of the cluster by the expected prevalence of the cluster (the product of the prevalence of each individual disease in the cluster).

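### The default in section 5.3 counts a hospital contact that cannot be seen without HES linkage as no contact, and about 61% of Phase 2 patients are unlinked; this matters mainly for food allergy and anaphylaxis severity

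*Protocol*

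**What the plan says.** Protocol section 5.3 sets two defaults. For activity, "A comorbidity will be defined as inactive in the year prior to the index date if it was not classified as active". For severity, "a comorbidity will be defined as mild in the year prior to the index date if it was not classified as moderate/severe". Neither makes an exception for patients without hospital data.

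The criteria for each condition follow as separate sentences, with no AND or OR between them. Eight of the nine moderate/severe definitions mention secondary care. For anaphylaxis the first criterion is "A secondary care consultation, ER attendance or hospital admission in the past year", and the only other is an adrenaline prescription.

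On the data, section 6.1 says "Approximately 220000 OPCRDR patients and 440000 CPRDR patients with active asthma will be available for inclusion in this phase" and puts the HES-linked number at about 260,000, all within CPRD. Section 4.1 states that "The HES records from the CPRD are required to identify secondary care service use and costs, and for some measures of disease severity", and section 6.1 repeats this. Section 6.4 accepts that in Phase 1 the activity and severity distinctions cannot be made for every comorbidity without linked HES. For Phase 2 it says that the numbers inactive, active, mild and "moderate/severe will be tabulated for each comorbidity using the primary care and linked HES data". Section 6.6 then examines each cluster by comorbidity severity and activity. Sections 5.4 and 6.7 restrict secondary care resource use and costs to linked patients. No such restriction is written for comorbidity activity or severity.

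**The concern.** A default of mild or inactive is sound when every criterion can be observed. Where a hospital contact cannot be seen, not classified as moderate/severe covers two states: no contact took place, or a contact took place but is not in the data. Section 5.3 treats both as mild.

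The error runs one way, towards mild or inactive, and its frequency depends on whether the patient is linked. Comorbidity severity and activity are among the features by which Phase 2 characterises clusters. If linked and unlinked patients are pooled, moderate/severe prevalence is understated, and being mild becomes partly a marker of database and linkage status. Comparisons between severity groups would then be mixed with data source. The protocol recognises the limit in sections 4.1, 6.1 and 6.4, but applies the remedy only to secondary care use and costs.

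**Working it through.** **Share unlinked.** Inputs from section 6.1: OPCRD 220,000; CPRD 440,000; linked 260,000. The protocol states no unlinked percentage, so this is derived.

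- Total: 220,000 + 440,000 = 660,000.
- Unlinked: 660,000 − 260,000 = 400,000, made up of 220,000 OPCRD and 180,000 CPRD.
- Share: 400,000 / 660,000 = 60.6%. Linked: 39.4%.

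This assumes that nobody is in both databases. With an overlap of v patients, the share is (660,000 − v − 260,000) / (660,000 − v):

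- v = 50,000: 350,000 / 610,000 = 57.4%
- v = 100,000: 300,000 / 560,000 = 53.6%
- v = 220,000: 180,000 / 440,000 = 40.9%

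**Which conditions the defaults can reach (section 5.3).**

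- Inactive: five conditions are always active (chronic rhinosinusitis, nasal polyps, food allergy, eosinophilic oesophagitis, anaphylaxis). That leaves four: atopic dermatitis, allergic rhinitis, urticaria and allergic conjunctivitis. All four accept a GP consultation.
- Mild: eosinophilic oesophagitis is always moderate/severe, which leaves eight.
- Of those eight, six (atopic dermatitis, allergic rhinitis, chronic rhinosinusitis, nasal polyps, urticaria, allergic conjunctivitis) accept a primary or a secondary care consultation, listed beside a prescription criterion.
- Only food allergy and anaphylaxis have a criterion that hospital contact alone can meet. Nasal polyps also lists a past polypectomy. Section 5.3 does not say which record this comes from, so it is not counted here.

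**Dependence on the connector.**

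- If AND: an unlinked patient can be moderate/severe for food allergy or anaphylaxis only where the hospital contact is coded in the GP record. In the extreme where none is coded, every true case among the unlinked is missed and pooled sensitivity is 1 − 0.606 = 39.4%.
- If OR: adrenaline is enough for anaphylaxis. For food allergy, a GP consultation, adrenaline or past anaphylaxis is enough. Only patients with hospital evidence and nothing else are missed.

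**Illustration (assumed values, not in the documents).** Let s be the share of true moderate/severe cases visible only through hospital contact. Assume no overlap, complete detection in linked patients and a true moderate/severe prevalence p = 20%. Pooled sensitivity is 1 − 0.606s. Observed pooled prevalence is p(1 − 0.606s). The spurious linked-versus-unlinked odds ratio is [p/(1 − p)] / [p(1 − s)/(1 − p(1 − s))].

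| s | pooled sensitivity | observed prevalence | odds ratio |
|---|---|---|---|
| 5% | 97.0% | 19.4% | 1.07 |
| 10% | 93.9% | 18.8% | 1.14 |
| 20% | 87.9% | 17.6% | 1.31 |
| 30% | 81.8% | 16.4% | 1.54 |

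**The case against.** The strongest reply is that hospital contact is mostly an alternative route. Six conditions accept a GP consultation, and the prescription criteria are in the GP record. This stands, and it limits the point. A reader might infer that activity and severity in general need hospital contacts, or that the whole unlinked 61% is scored inactive or mild. Section 5.3 does not support either inference: only unlinked patients with no other qualifying evidence are affected.

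A second reply is that hospital contacts may be coded in GP records. The protocol seems to expect some of this, since the asthma control measure in section 5.1 uses A&E, inpatient and outpatient contacts and is reported in the OPCRD-only Phase 1. This would reduce the effect, but nothing shows that such coding is complete, and sections 4.1 and 6.1 say that HES is required for some severity measures.

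A third reply is that the section 6.4 wording on linked HES data already means the linked population. It can be read that way, but it names data sources, not patients. Where the protocol intends a restriction (sections 5.4 and 6.7), it says so, and section 6.6 has no such phrase.

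A fourth reply is that denominators can wait for the Phase 2 table list (section 6.6), the ISAC application (section 7.0) or the SAP. That is fair for table layout. It does not cover the default, which section 5.3 already fixes.

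Lastly, HES is not a perfect standard: section 5.3 notes that outpatient reasons are not routinely coded there and will be attributed to the nearest diagnosis in time. This stands, and it is a reason to accept a uniform primary-care-only definition as an alternative remedy.

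**Conclusion.** The point holds in limited form. As written, the plan has no not-ascertainable category and does not restrict comorbidity activity and severity to linked patients or stratify them by linkage. The resulting misclassification goes towards inactive or mild and differs by data source.

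The pool in which it can occur is 60.6% of Phase 2 patients with no overlap between databases, falling to 40.9% with full overlap. The number actually misclassified is a subset that the documents do not quantify. It should matter mainly for food allergy and anaphylaxis severity and less for the other six conditions. It cannot affect activity in the five always-active conditions or severity in eosinophilic oesophagitis. For food allergy and anaphylaxis it could range from small (OR) to near total among the unlinked (AND, with no GP coding of hospital contacts). The percentages in the illustration rest on assumed shares and should not be read as estimates of the bias in this study.

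**What to change.** In sections 5.3, 6.4 and 6.6:

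1. State whether the listed criteria for each condition are joined by AND or OR.
2. State that Phase 2 activity and severity results that use hospital criteria are produced in the HES-linked CPRD patients (about 260,000), at minimum for food allergy and anaphylaxis severity. For unlinked patients, report a separately labelled version based on primary care data only. Alternatively, apply one primary-care-only definition to everyone and report it by linkage status.
3. Do not pool linked and unlinked classifications under the default. Where a criterion cannot be observed, do not let the default assign mild or inactive.

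The cost is some protocol wording, one extra set of tables and, under the first option, a smaller population for these results: about 260,000 of 660,000 (39.4%), which is still large for descriptive work. The primary-care-only alternative keeps all patients but gives up the hospital evidence.

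### Section 5.3 states no and/or between its criteria and does not tie severity to activity, so mild pools inactive with active-mild disease and urticaria can be inactive yet moderate/severe

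*Protocol*

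**What the plan says.** Section 5.3 sets up two binary axes: "Many of the comorbidities can be further characterised as inactive or active, and mild or moderate/severe at the index date". Each is closed by taking a complement: "A comorbidity will be defined as inactive in the year prior to the index date if it was not classified as active", and "a comorbidity will be defined as mild in the year prior to the index date if it was not classified as moderate/severe".

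The criteria for each disease then follow as separate sentences with no connective. For atopic dermatitis they are "Active: A primary or secondary care consultation in the previous year. Prescription of a topical corticosteroid in the previous year" and "Moderate/severe: A primary or secondary care consultation in the previous year. Prescription of a medium- to high-potency topical corticosteroid in the previous year". For allergic rhinitis the first list is "Active: A primary or secondary care consultation in the previous year. Prescription of a nasal corticosteroid in the previous year"; the moderate/severe list repeats the consultation item and asks for three or more nasal corticosteroids. Allergic conjunctivitis has the same structure with eye drops.

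For urticaria, activity looks back two years for a consultation and one year for an antihistamine. Severity looks back one year for a consultation and over the whole record for "A double or greater dose of an oral antihistamine at any time prior to the index date".

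The other five diseases are always active. Two of them carry a lifetime severity item: polypectomy for nasal polyps and anaphylaxis for food allergy.

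Section 6.4 has all four labels tabulated for each comorbidity in phase 2, and section 6.6 has the selected clusters described by comorbidity severity and activity.

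**The concern.** A severity label is useful if moderate/severe and mild differ in the burden of current disease. Four features of 5.3 work against that.

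- Mild takes in disease with no sign of activity.
- The consultation item appears under both headings, so whether it separates the levels depends on a connective that is not given.
- Some severity items cover the whole record, although the label is defined for the year before the index date.
- The potency wording for atopic dermatitis does not match the classes in Appendix 6, to which it refers.

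Two programmers could follow the text faithfully and produce different phase 2 tables. A contrast between mild and moderate/severe could reflect who was seen, or who had quiescent disease, rather than severity.

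**Working it through.** The protocol gives no figure to reproduce, so the check is an enumeration of the rules as written.

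**Inputs (section 5.3).** Levels per disease:
- Atopic dermatitis: consultation in the last year (no, yes) × topical steroid (none, low, medium/high) = 2 × 3 = 6.
- Allergic rhinitis: consultation (no, yes) × nasal steroids (0, 1, 2, 3 or more) = 2 × 4 = 8.
- Allergic conjunctivitis: consultation (no, yes) × eye drops (0, 1, 2 or more) = 2 × 3 = 6.
- Urticaria: consultation (none in two years, year 2 only, last year) × antihistamine in the last year (no, yes) × double dose ever (no, yes) = 3 × 2 × 2 = 12.

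**Rule.** *Any one*: a label applies if at least one listed item is met. *All*: it applies only if every item is met. The same connective is used for both lists of a disease. Inactive and mild are the complements. The table counts combinations, not patients.

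| Disease | Reading | Inactive, mild | Active, mild | Active, mod/severe | Inactive, mod/severe | Total |
|---|---|---|---|---|---|---|
| Atopic dermatitis | any one | 1 | 1 | 4 | 0 | 6 |
| | all | 4 | 1 | 1 | 0 | 6 |
| Allergic rhinitis | any one | 1 | 2 | 5 | 0 | 8 |
| | all | 5 | 2 | 1 | 0 | 8 |
| Allergic conjunctivitis | any one | 1 | 1 | 4 | 0 | 6 |
| | all | 4 | 1 | 1 | 0 | 6 |
| Urticaria | any one | 1 | 3 | 7 | 1 | 12 |
| | all | 7 | 3 | 1 | 1 | 12 |

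**(a) Mild includes inactive.** The inactive-mild cell is filled in every row. A patient who meets no item is inactive and mild whatever the connective. If all items are required the cell grows, for example to 5 of the 7 mild combinations in rhinitis (5 + 2 = 7).

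**(b) The shared consultation.** Under *any one*, every combination with a consultation in the last year is active and moderate/severe in all four diseases. Active-mild is left to patients not seen in that year, such as those with one or two nasal steroids only. Chronic rhinosinusitis and nasal polyps, being always active, become moderate/severe on a consultation alone. Under *all*, the prescription item separates the levels in atopic dermatitis, rhinitis and conjunctivitis (consultation plus one or two nasal steroids is active-mild; plus three or more is moderate/severe). But nasal polyps then need a consultation, three nasal steroids and polypectomy, and food allergy needs all four items, including anaphylaxis.

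**(c) Urticaria and lifetime items.** Inactive with moderate/severe arises in urticaria only:
- *Any one*: no consultation in two years, no antihistamine in the last year, a double dose at some time.
- *All*: consultation in the last year, no antihistamine in that year, a double dose at some time.

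Nasal polyps and food allergy cannot be inactive. There the narrower mismatch is that a lifetime event sets the label alone (*any one*) or is a condition for it (*all*), while 5.3 defines the label for the year before the index date.

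**(d) Potency.** Appendix 6 has four classes: Ultra-high, High, Moderate and Low. The 5.3 wording spans medium to high. Read literally, a patient prescribed only an Ultra-high preparation fails the potency item. Under *all* that patient is always mild; under *any one*, only if there was no consultation in the last year.

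**The case against.** The strongest reply is that 5.3 defines two separate axes, each exhaustive and mutually exclusive, so an inactive-mild patient is no contradiction and the axes can be cross-tabulated. That is fair, and five of the nine diseases are always active, so no pooling arises in them. But section 6.4 lists the four labels without calling for a cross-tabulation, and a severity table alone would pool.

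Second, the shared consultation collapses the levels only under *any one*, which the protocol does not state. There is also a mixed reading: any one item for active, all items for moderate/severe. It would separate the levels and remove the urticaria contradiction, since inactive would then require no consultation in two years and moderate/severe would require one in the last year. That stands, but nothing in the text selects this reading. It would still leave inactive disease in mild and the long conjunctions for nasal polyps and food allergy.

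Third, a connective could be settled in an SAP. However, 5.3 presents these as the adopted definitions, and whether severity depends on activity is part of the definition.

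Four stronger readings are tempting but are not supported:
- *Polypectomy or past anaphylaxis turns inactive disease moderate/severe.* It cannot, because both diseases are always active.
- *Eye drops for unrelated disease inflate conjunctivitis.* The item "Two or more prescriptions of any topical eye drop in the previous year" is broad, but 5.3 assigns a drug with several indications to the diagnosis nearest in time to its initiation. That note is framed for overlap among the study diseases, so it covers the point only in part.
- *The Ultra-high class is deliberately excluded.* Appendix 6 has no class called medium, so loose drafting is as likely.
- *Resource-use gradients by comorbidity severity are biased.* Section 6.7 models comorbidity patterns and states no such gradient.

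**Conclusion.** The point holds for the definitions. Mild pools inactive with active-mild disease in four of the nine comorbidities under any connective. Urticaria can be inactive and moderate/severe if one connective governs both of its lists, whichever it is. The remaining consequences depend on a connective that 5.3 omits.

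The size in patients cannot be derived. A reader might infer that the two readings differ many-fold, but the protocol gives no rates to support a figure. Assume, for rhinitis, 25% consulting, 20% with at least one nasal steroid and 8% with at least three:

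- Independent: active 1 − 0.75 × 0.80 = 40% against 0.25 × 0.20 = 5%; moderate/severe 1 − 0.75 × 0.92 = 31% against 0.25 × 0.08 = 2%.
- Prescriptions nested within consulters: active 25% against 20% (25/20 = 1.25-fold); moderate/severe 25% against 8% (25/8 = about 3-fold).

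These rates are invented and the ratios turn on the dependence assumed, so no fold difference is claimed.

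The reach is limited to the phase 2 descriptions by comorbidity severity and activity (sections 6.4 and 6.6). Phase 1 prevalence is unaffected: section 5.2 identifies comorbidities by Read code (plus adrenaline prescription for anaphylaxis), without these categories. The phase 2 objective in section 2.2 does not name comorbidity severity, although the protocol's opening summary of aims does.

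**What to change.** Before phase 2 coding, revise section 5.3 as follows:

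1. State the connective for every list, disease by disease.
2. Assign severity only to active disease, giving one ordered variable (inactive, active-mild, active-moderate-or-severe); or keep the two axes and require their cross-tabulation in section 6.4.
3. Do not let a primary-care consultation that already establishes activity suffice by itself for moderate/severe.
4. Reconcile the urticaria look-back windows, and reconcile the lifetime items for urticaria, nasal polyps and food allergy with the one-year definition of the label. Which window or threshold is clinically right is for the study team.
5. Align the potency wording with the class names in Appendix 6 and say expressly how the Ultra-high class is treated.

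The cost is a rewrite of one section, the matching table shells and the classification code. No new data are needed.

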2.2 Study objectives

Phase 1: The primary objective is to estimate the frequency of each combination/cluster of T2 type comorbidities in a real world active asthma population, and to select, by consensus, a limited set of common comorbidity clusters for further investigation.

Phase 2: The primary objective is to describe the overlap between these clusters and between individual comorbidities within the clusters in terms of patient demography, and asthma severity, resource utilisation and costs.

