6.6 Characterisation of selected comorbidity clusters (phase 2)

The associations between the individual diseases in the selected clusters will be illustrated in graph format (appendix 11). This will show which diseases are often diagnosed together. An edgelist, a list of all disease pairs in the clusters, will be used to calculate the position of each disease in two-dimensional space using a multidimensional scaling procedure.

This will include an investigation of the characteristics of each cluster by comorbidity severity and activity, eosinophil count and age. Patient demography and asthma severity will also be compared within and between these key comorbidity clusters. Associations between specific co-morbidity patterns and disease severity will be estimated using logistic regression, adjusting for confounders.

The list of tables and figures to be produced will be finalised at the beginning of phase 2.

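### Crediting shared treatment to a single diagnosis (5.3) lowers per-disease severity, and allergic rhinitis activity, by construction in patients with overlapping airway comorbidities, and no sensitivity analysis varies the rule

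*Protocol*

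**What the plan says.** Protocol 5.3 recognises that "some medications can be indicated for more than one of the comorbidities of interest" and resolves this by giving each such drug one indication: "the diagnosis recorded closest in time to the initiation of the medication will be taken as the indication". For hospital outpatient visits to a specialty that treats several of the diseases, with ENT as the protocol's own example, it says: "we will attribute the outpatient consultation to the diagnosis recorded closest in time to the secondary care consultation". Drugs are thus anchored at initiation and visits at the visit date, and each gets one diagnosis.

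A disease that receives no credit is not set to unknown. On activity, "A comorbidity will be defined as inactive in the year prior to the index date if it was not classified as active". On severity, "a comorbidity will be defined as mild in the year prior to the index date if it was not classified as moderate/severe".

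The disease definitions in 5.3 give allergic rhinitis, chronic rhinosinusitis and nasal polyps the same prescription threshold for moderate/severe: three or more nasal corticosteroids in the previous year. A nasal corticosteroid prescription also bears on whether allergic rhinitis is active. The other two diseases are always active.

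These categories are used in Phase 2. Section 6.4 tabulates them for each comorbidity, and 6.6 says of the selected clusters: "This will include an investigation of the characteristics of each cluster by comorbidity severity and activity, eosinophil count and age". The only sensitivity analysis in 6.9 restricts the analysis to patients with at least five years of record.

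**The concern.** The attribution rule has no effect on nasal corticosteroid credit in a patient with one of the three airway diseases. It removes credit in a patient with two or three. The resulting error depends on the number of sharing diseases, which is what distinguishes the clusters being described. A patient with rhinitis alone and three nasal corticosteroid prescriptions meets the prescription criterion for moderate/severe rhinitis. A patient with the same prescribing, and polyps coded nearer to the start of the drug, gets no prescription credit for rhinitis, which may then fall to inactive and mild.

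Anchoring at initiation adds a second problem for drugs. The criteria concern the previous year, but the attribution may rest on a diagnosis made long before. Polyps coded after a nasal corticosteroid was started for rhinitis gain nothing from that drug, however often it is prescribed in the assessment year.

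At stake is the reading of the Phase 2 activity and severity results. Overlap clusters could appear to carry milder disease, component by component, than single-disease clusters because of how credit is allocated.

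**Working it through.** The protocol gives no figure for misclassification, and 6.1 only counts available patients, so there is nothing to reproduce. What follows is an illustration on assumed inputs.

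**Inputs**
- From 5.3: one credit per shared drug; the same three-prescription threshold for the three airway diseases; uncredited diseases default to mild.
- Assumed: p, the share of patients with three or more nasal corticosteroid prescriptions in the year; c, the share meeting the consultation criterion, independent of p and outside the attribution rule; k, the number of airway diseases sharing the drug, with credit falling on each equally often. True prescribing is the same in single-disease and overlap patients, so the true odds ratio is 1.

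**Prescription criterion alone.** The chance that a given disease meets it falls from p to p/k. For k = 2, apparent OR = [(p/2)/(1 − p/2)] / [p/(1 − p)].

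**With consultation as an alternative criterion.** The share moderate/severe is 1 − (1 − c)(1 − p/k), against 1 − (1 − c)(1 − p) with full credit. The table uses k = 2 and c = 0.3.

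| p | Prescription only: split vs full | OR | With c = 0.3: split vs full | OR |
|---|---|---|---|---|
| 0.20 | 0.10 vs 0.20 | 0.111/0.250 = 0.44 | 0.370 vs 0.440 | 0.587/0.786 = 0.75 |
| 0.30 | 0.15 vs 0.30 | 0.176/0.429 = 0.41 | 0.405 vs 0.510 | 0.681/1.041 = 0.65 |
| 0.50 | 0.25 vs 0.50 | 0.333/1.000 = 0.33 | 0.475 vs 0.650 | 0.905/1.857 = 0.49 |

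At c = 0.6 the same formula gives 0.84, 0.75 and 0.58.

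**Absolute loss, alternative criteria.** The loss is (1 − c) × p × (1 − 1/k). Over p = 0.2 to 0.6 and c = 0.1 to 0.6:
- k = 2: from 0.4 × 0.2 × 1/2 = 4 points to 0.9 × 0.6 × 1/2 = 27 points.
- k = 3: from 0.4 × 0.2 × 2/3 = 5 points to 0.9 × 0.6 × 2/3 = 36 points.

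**Joint criteria.** If the criteria must all be met, the share is c × p/k, so it is divided by k. At p = 0.4 and c = 0.3, it is 12% with full credit, 6% for k = 2 and 4% for k = 3.

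For k = 1 every loss is zero. The direction is the same under either reading of how the criteria combine; only the size changes.

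**The case against.** The strongest reply is that 5.3 adopts the rule after reviewing published approaches, and that the alternative has its own bias. If every disease is credited, one nasal corticosteroid meets the identical threshold for rhinitis, rhinosinusitis and polyps at once. Prescription-based severity could then be inflated in the overlap clusters. Nothing in the documents shows which rule is nearer the truth. This stands, and it is why the closest-diagnosis rule should not simply be replaced. It does not remove the dependence of the current error on cluster, or show its size.

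Several stronger readings are tempting but unsupported:

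- A reader might infer that the whole Phase 2 cluster comparison is distorted. Section 2.2 does set out to "describe the overlap between these clusters and between individual comorbidities within the clusters", but its terms are demography, asthma severity, resource use and costs. Airway cluster membership rests on Read codes (5.2). Asthma severity (5.1) and asthma-related resource use and cost (5.4) do not use the rule.
- A reader might infer that every prescription or visit is affected, all fixed at initiation. The rule covers only shared-indication drugs and shared-specialty outpatient visits, and visits are dated by the visit.
- A reader might infer lower activity across the board. Of the three airway diseases, only allergic rhinitis can change activity.
- A reader might extend the argument to adrenaline in food allergy with anaphylaxis. Food allergy is also moderate/severe on any history of anaphylaxis. If the criteria are alternatives, it therefore keeps that status whichever disease is credited with the adrenaline.

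The odds ratios on prescriptions alone are also the extreme case under alternative criteria. Polypectomy and primary care consultations lie outside the attribution rule and can qualify a patient without it if the criteria are alternatives.

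**Conclusion.** The point holds within limits. For allergic rhinitis, chronic rhinosinusitis and nasal polyps, moderate/severe status based on prescriptions or outpatient visits is lower in overlap patients than in single-disease patients with the same care. The same applies to activity for allergic rhinitis only. This affects the Phase 2 tabulation in 6.4, the cluster characterisation in 6.6, and any model that uses these categories. The logistic regression in 6.6 could be one such model, since it does not say whether its disease severity outcome refers to asthma or to the comorbidity.

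The direction follows from the text; the size does not. For two diseases the illustrations run from an apparent odds ratio of 0.33 (p = 50%, prescriptions alone) to 0.84 (p = 20%, an assumed 60% qualifying by consultation as an alternative). They rest on assumed p and c, an even split of credit, independence of the two criteria, and equal prescribing in single-disease and overlap patients. Section 5.3 does not say whether its listed criteria are joint or alternative, so the range cannot be narrowed from the document.

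**What to change.** Keep the closest-diagnosis rule in 5.3 as the main analysis. Add to 6.9 a sensitivity analysis along these lines:

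*The Phase 2 comorbidity activity and severity results will be repeated with each shared-indication prescription and each shared-specialty outpatient visit credited to every comorbidity for which 5.3 lists it and whose first code precedes that prescription or visit. Differences in comorbidity severity or activity between single-disease and overlap clusters will be interpreted only where both rules agree.*

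The cost is a short addition to the text and one further reclassification run on data already held. The downside is that the all-credit rule may over-attribute in overlap clusters. The two sets of results should therefore be presented side by side as a range, with neither taken as the correct value.
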